### I. Research Objectives/Background

#### 1. Background

Open tibia fractures are at high risk for deep infection (Tornetta et al.). Irrisept is a wound irrigant that has been used to lower infection rates in different wound settings. To the investigators' knowledge, there are no robust data showing its effectiveness at lowering infection rates in open tibia fracture management. Therefore, the primary purpose of this study is to determine the effects of Irrisept versus normal saline on deep infection rate following treatment of open tibial fractures. Secondly, we will perform subcohort analyses to assess the effects of severity grade (type I vs II vs II open) on deep infection rates in open tibia fractures.

#### 2. Research Objectives

- a. Primary
  - i. 90-day surgical site infection (SSI) incidence
- b. Secondary
  - i. Fracture healing at 6 months
  - ii. PROMIS and VAS patient reported outcomes

### II. Drugs/Biologics

1. This study is designed to prospectively compare post-operative infection rates in patients treated for open tibia fractures and wounds irrigated with one of two solutions.
2. Patients will be randomized to one of the two treatments:
  - i. Normal Saline
  - ii. Irrisept
3. Patients with open tibia fractures will undergo standard operative debridement and appropriate fixation based on the severity and contamination of the fracture.
4. Normal saline is a mix of sodium chloride and sterile water. It has a number of uses in medicine including cleaning wounds.

5. Irrisept is a wound debridement and cleansing lavage system. It contains low concentrations of Chlorhexidine Gluconate (CHG) 0.05% in sterile water. One bottle contains 450 mL 0.05% CHG in sterile water, USP 99.95%. Irrisept is cleared as a Class II Medical Device and an unclassified Combination Product. It can be used as SOC to washout open tibia fractures.

### **III. Recruitment Process**

1. Recruitment will take place in a private space in the University of Missouri Health System, after identifying a patient over the age of 18 who has an open tibial fracture.
2. Potential participants will be pre-screened initially via medical record/PowerChart/they will then be screened in person to ensure all entry criteria are met.

### **IV. Consent Process**

1. Consent will be obtained from the potential study subject him or herself. Properly trained and authorized personnel from the research staff or the treatment team will present the study to the potential subject, give them the informed consent to read, review the consent document with the subject and allow them time to consider participation and ask questions. The potential subject will sign and date the informed consent prior to any research activity.

### **V. Inclusion/Exclusion Criteria**

1. Inclusion
  - a. Adult, 18 or over
  - b. Open tibia fracture
  - c. Able to obtain informed consent from patient
2. Exclusion
  - a. Minor, under 18
  - b. Pregnancy
  - c. Prisoner
  - d. Allergic to chlorhexidine gluconate
  - e. Unable to provide informed consent

### **VI. Number of Subjects**

1. We plan to enroll 230 participants (n=230 subjects) (100 subjects per group, 30 screen fails) for a 2-year study. This will allow complete data for at least 200 who will complete the one-year follow-up.
2. This sample size was determined by a pre-study power analysis based on 10% reduction in 90-day SSI incidence with a desired power of 0.8 and alpha set at <0.05.

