### **VII. Study Procedures/ Design/Treatment Plan**

1. Randomization Process
  - a. After informed consent is obtained, all patients who meet eligibility criteria will be randomized into one of two groups. Randomization will be achieved by numbering 230 sealed envelopes (115 Irrisept, 115 Normal Saline). There is no blinding to the randomization. It would be difficult to blind the participants or research personnel.
  - b. Standard of care at this institution is irrigation with normal saline and debridement.
  - c. If randomized to the Irrisept group, patients will be removed from standard of care.
2. Surgery
  - a. Patients will be screened and randomized prior to going to the operating room for the initial operative debridement of the open tibia fracture. They will return to the operating room for as many operative debridements as necessary until the definitive fixation surgery is performed.
  - b. One group will utilize only Irrisept solution for all open fracture debridements and irrigations, and the other will utilize only normal saline for all debridements and irrigations. Surgical sites that are not the open fracture site should be irrigated with normal saline as per standard of care.
  - c. The subjects will undergo standard operative debridement and fixation.
  - d. All other components of the management will be standard—antibiotics pre- and postop, surgical debridement, dressings/use of negative pressure wound therapy, etc.
3. Clinical Follow-Up
  - a. Standard of Care Standard of Care (SOC)—2 weeks, 6 weeks, 3 months, 6 months and 1 year with tibia radiographs at each visit except the 2-week follow up. Study window will be +/- 2 weeks starting at the 6-week visit.
  - b. Tibia radiographs will be collected at each visit per SOC to assess fracture healing as 0-not healed; 1-partially healed; or 2-completely healed.
  - c. Deep infection rate as well as wound healing will be assessed. Developing infection would be monitored regardless of the subject's participation in the study.
  - d. Patient reported outcomes including PROMIS and VAS pain scores will be collected at each visit per SOC.
  - e. Subjects will be monitored at follow-ups for unanticipated events.
4. Subjects will be removed if they do not return to their follow-up visits or do not complete the study specific tasks.
5. Subjects that are removed prematurely or complete the study will continue routine care per physician's standard of care treatment.

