6. No specimens will be collected for research purposes.
7. Statistical Analysis – significance set at  $p < 0.05$ .
  - a. Primary Outcome Measure: CDC-defined 90-day surgical site infection (SSI) incidence – compared among groups using chi-square test.
  - b. Secondary Outcome Measure: Fracture healing at 6 months post-op – compared between groups using a rank sum test.

- c. Secondary Outcome Measures: PROMIS and VAS Pain scores – compared between groups using unpaired t-Tests.
- d. Secondary Outcome Measure: Multivariate analyses will be used to assess the effects of severity grade (type I vs II vs II open) on deep infection rates in open tibia fractures.

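### Sections VI.1 and VII.1.a disagree on whether 200 or 230 patients are randomised, and on VI.1's own breakdown at least 200 one-year completers requires zero loss

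*Combined protocol and SAP*

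**What the plan says.** Section VI.1 plans to enrol 230 and breaks this down as "100 subjects per group, 30 screen fails". It then adds: "This will allow complete data for at least 200 who will complete the one-year follow-up".

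Section III.2 places the eligibility check before randomisation: after a record pre-screen, "they will then be screened in person to ensure all entry criteria are met". Section VII.1.a follows the same order. After consent, "all patients who meet eligibility criteria will be randomized into one of two groups", and the allocation is made by "numbering 230 sealed envelopes (115 Irrisept, 115 Normal Saline").

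Section VII.4 expects some patients to leave: "Subjects will be removed if they do not return to their follow-up visits". No section gives a loss rate, a number randomised at which recruitment stops, or a statement that some envelopes are spares.

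**The concern.** Two things do not fit. First, a screen failure by definition fails the entry criteria, and VII.1.a randomises only those who meet them. The 30 screen failures in VI.1 should therefore never reach an envelope, yet the envelope count equals the full 230. Someone preparing envelopes would plan for 115 per arm, while someone reading VI.1 would plan for 100 per arm.

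Second, if 200 are randomised, the promise of at least 200 one-year completers leaves no room for a single loss, in a trial that provides for removing patients who miss visits.

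Two things are at stake. The stated completer count is one that VI.1's breakdown cannot be expected to deliver. And in a trial without blinding, the number randomised at which recruitment ends should be fixed in advance, whereas here it could be read as 200 or 230.

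**Working it through.** **Inputs.** From VI.1: 230 enrolled, 100 per group, 30 screen failures, at least 200 one-year completers. From VII.1.a: 115 + 115 envelopes, eligible patients only. From XI.3: $65 x 200 = $13,000, with two bottles per case. The documents give no loss rate, so every loss rate below is an assumption.

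**The plan's own totals.** Both are internally exact:
- VI.1: 2 x 100 + 30 = 230 enrolled, hence 230 - 30 = 200 in the arms.
- VII.1.a: 115 + 115 = 230 allocations.

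The totals match, but they count different people. VI.1 does not use the words 200 randomised; that figure follows from 100 per group together with VII.1.a's restriction to eligible patients.

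**Loss compatible with 200 completers**, 1 - 200/N:
- N = 200: 1 - 200/200 = 0%.
- N = 230: 1 - 200/230 = 30/230 = 13.0%.

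**Expected completers**, N x (1 - d), and the number randomised needed for 200 completers, 200/(1 - d) rounded up:

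| Assumed one-year loss d | 200 randomised | 230 randomised | N needed for 200 |
|---|---|---|---|
| 5% | 190 | 218.5 | 211 |
| 10% | 180 | 207 | 223 |
| 15% | 170 | 195.5 | 236 |
| 20% | 160 | 184 | 250 |

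**Chance that all 200 complete**, (1 - d)^200, with independent losses: 0.134 at d = 1%, 0.0176 at 2%, 0.000035 at 5%.

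**If the extra 30 envelopes are spares.** Suppose recruitment stops at 200 and the 230 envelopes are fully shuffled (an assumption; VII.1.a describes neither shuffling nor blocking). The Irrisept count is then hypergeometric with mean 100 and variance 200 x 0.5 x 0.5 x (230 - 200)/(230 - 1) = 6.55, so the SD is 2.56. The chance of exactly 100 is 0.155, and of 95 to 105 is 0.970. The imbalance is small, but the arms are not fixed at 100 each.

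**Cross-check with the budget.** If the 200 in XI.3 are bottles, 200/2 = 100 Irrisept cases. That agrees with VI.1 and not with 115 per arm. The wording of XI.3 does not settle whether the 200 are bottles, so this is supporting evidence only.

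**The case against.** The strongest reply is that VI.1 never says 200 randomised. One can read the plan as 230 randomised, about 30 lost and at least 200 completing. That fits the enrolment total, the envelopes and the completer promise, carries a 13.0% loss allowance, and reduces the fault to one loosely used term. A second reply is that the extra 30 envelopes are spares.

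Both readings are possible, but the documents state neither. The first requires screen failures to mean losses after randomisation and 100 per group to mean completers; it also sits badly with the budget if the 200 are bottles. The second explains the envelopes but leaves the 0% loss problem untouched.

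The objection about reach stands in large part. The primary outcome is "CDC-defined 90-day surgical site infection (SSI) incidence", fracture healing is tested at 6 months, the PROMIS and VAS tests name no time point, and nothing in VII.7 names one year. The primary test is affected only by losses before day 90 or by leaving removed patients out of the analysis. Section VII.3.c suggests infection may still be seen after removal: "Developing infection would be monitored regardless of the subject's participation in the study". VI.2 gives no control infection rate, so the documents do not allow an effect on power to be calculated, and none is claimed here.

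**Conclusion.** The point holds. VI.1 and VII.1.a give incompatible accounts of the same 30 people, and this needs only the current text and addition to see. On VI.1's breakdown, at least 200 one-year completers requires 0% loss; assumed losses of 5% to 15% would leave 190 to 170. On the envelope count, the same target would tolerate 13.0% loss.

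The mismatch is certain. Which number was intended is not: 200 randomised is the better-supported reading, from 100 per group, the term screen failures and, if the 200 in XI.3 are bottles, the budget. The consequence is moderate. A stated size is not delivered by the plan's own breakdown and the recruitment end point is ambiguous, but no planned test is tied to one year. The plan should be corrected; the design is not undermined.

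**What to change.** The sponsor should confirm what the 30 represent, then make VI.1, VII.1.a and XI.3 agree.

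**Default: 230 enrolled, 200 randomised.**
- In VII.1.a, either prepare 200 envelopes (100 per arm), or state that the extra 30 are unused spares, that recruitment stops at 200 randomised, and that arm sizes may then differ slightly from 100.
- In VI.1, replace the completer promise with the number expected at one year under a named loss assumption (for example 190 at 5%, 180 at 10%, 170 at 15%), and add the number expected to be evaluable at day 90 for the primary test.

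This costs about one sentence in each section and adds no patients or product. The completer figure becomes less favourable. With exactly 100 + 100 shuffled envelopes, the last 2 x 100/101 = 1.98 allocations on average become predictable to anyone keeping count.

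**Alternative, only if the 30 were meant as losses after randomisation.** Reword VI.1 to 230 randomised, 115 per arm, with a 13% loss allowance, and state screen failures on top of the 230. The documents give no screen-failure number for this reading; if it were again 30, enrolment would be 230 + 30 = 260. Relative to the default, this means 30 more randomised patients within the 2-year study. XI.3 must also be rechecked: if its 200 are bottles, the product cost becomes 115 x 2 x $65 = $14,950 instead of $13,000, a difference of $1,950.

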### **VII. Study Procedures/ Design/Treatment Plan**

1. Randomization Process
  - a. After informed consent is obtained, all patients who meet eligibility criteria will be randomized into one of two groups. Randomization will be achieved by numbering 230 sealed envelopes (115 Irrisept, 115 Normal Saline). There is no blinding to the randomization. It would be difficult to blind the participants or research personnel.
  - b. Standard of care at this institution is irrigation with normal saline and debridement.
  - c. If randomized to the Irrisept group, patients will be removed from standard of care.
2. Surgery
  - a. Patients will be screened and randomized prior to going to the operating room for the initial operative debridement of the open tibia fracture. They will return to the operating room for as many operative debridements as necessary until the definitive fixation surgery is performed.
  - b. One group will utilize only Irrisept solution for all open fracture debridements and irrigations, and the other will utilize only normal saline for all debridements and irrigations. Surgical sites that are not the open fracture site should be irrigated with normal saline as per standard of care.
  - c. The subjects will undergo standard operative debridement and fixation.
  - d. All other components of the management will be standard—antibiotics pre- and postop, surgical debridement, dressings/use of negative pressure wound therapy, etc.
3. Clinical Follow-Up
  - a. Standard of Care Standard of Care (SOC)—2 weeks, 6 weeks, 3 months, 6 months and 1 year with tibia radiographs at each visit except the 2-week follow up. Study window will be +/- 2 weeks starting at the 6-week visit.
  - b. Tibia radiographs will be collected at each visit per SOC to assess fracture healing as 0-not healed; 1-partially healed; or 2-completely healed.
  - c. Deep infection rate as well as wound healing will be assessed. Developing infection would be monitored regardless of the subject's participation in the study.
  - d. Patient reported outcomes including PROMIS and VAS pain scores will be collected at each visit per SOC.
  - e. Subjects will be monitored at follow-ups for unanticipated events.
4. Subjects will be removed if they do not return to their follow-up visits or do not complete the study specific tasks.
5. Subjects that are removed prematurely or complete the study will continue routine care per physician's standard of care treatment.
6. No specimens will be collected for research purposes.
7. Statistical Analysis – significance set at  $p < 0.05$ .
  - a. Primary Outcome Measure: CDC-defined 90-day surgical site infection (SSI) incidence – compared among groups using chi-square test.
  - b. Secondary Outcome Measure: Fracture healing at 6 months post-op – compared between groups using a rank sum test.

- c. Secondary Outcome Measures: PROMIS and VAS Pain scores – compared between groups using unpaired t-Tests.
- d. Secondary Outcome Measure: Multivariate analyses will be used to assess the effects of severity grade (type I vs II vs II open) on deep infection rates in open tibia fractures.

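### Unblinded allocation before the first debridement, with no stated time for severity grading, leaves an avoidable risk of performance bias and arm-aware grading at the index operation

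*Combined protocol and SAP*

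**What the plan says.** All references are to the combined protocol and SAP.

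- **Timing (VII.2.a).** "Patients will be screened and randomized prior to going to the operating room for the initial operative debridement of the open tibia fracture".
- **Blinding (VII.1.a).** "There is no blinding to the randomization. It would be difficult to blind the participants or research personnel". The reason given concerns participants and research personnel. The operating surgeon is not mentioned.
- **Allocation (VII.1.a).** "Randomization will be achieved by numbering 230 sealed envelopes (115 Irrisept, 115 Normal Saline". Nothing says when an envelope is opened relative to the operation, other than that randomisation precedes theatre.
- **Surgery.** Section II.3 provides for "standard operative debridement and appropriate fixation based on the severity and contamination of the fracture". Section VII.2.a adds: "They will return to the operating room for as many operative debridements as necessary until the definitive fixation surgery is performed".
- **Other care (VII.2.d).** "All other components of the management will be standard—antibiotics pre- and postop, surgical debridement, dressings/use of negative pressure wound therapy, etc".
- **Severity (VII.7.d).** "Multivariate analyses will be used to assess the effects of severity grade" on deep infection. Section I.1 also announces subcohort analyses by grade. No section gives the time of grading, the assessor or the classification system.
- **Primary analysis (VII.7.a).** A chi-square comparison of 90-day surgical site infection (SSI) between arms, without covariates.

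**The concern.** The arms are meant to differ only in the irrigant. Debridement is a major co-intervention in the same operation and depends on judgement. If the surgeon knows the arm beforehand, the first debridement could be more or less thorough in one arm, and part of any SSI difference would then reflect surgery. Section VII.1.c describes the Irrisept arm as a departure from standard care, so there is a conceivable motive to compensate, in either direction.

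The second route concerns severity grade. A grade recorded after allocation by someone who knows the arm can drift with it. Any analysis that uses grade would then rest on a variable measured differently in the two arms.

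Both routes operate at the index operation. Blinding those who later assess infection would close neither.

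**Working it through.** **Step 1: what the sections establish together.** VII.2.a fixes allocation before the first debridement. VII.1.a says it is not blinded. No section keeps the arm from the surgeon until irrigant is used. VII.2.c and VII.2.d call debridement standard without criteria for its extent, and VII.2.a leaves the number of debridements to judgement. The route for performance bias is therefore open as written.

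**Step 2: which analyses each route can reach.**

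| Route | Chi-square primary test (VII.7.a) | Grade analyses (I.1, VII.7.d) |
|---|---|---|
| Debridement differs by arm | yes | yes |
| Grading differs by arm | no, grade is not in the test | yes |

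**Step 3: the plan's own figure.** The plan has no figure on this point. The only number borrowed below is 100 per group (VI.1). It cannot be reproduced uniquely, because VI.2 gives no control rate and does not say whether its 10% reduction is absolute or relative. If absolute, two-sided, at 12% versus 2%:

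n = [1.960·√(2·0.07·0.93) + 0.842·√(0.12·0.88 + 0.02·0.98)]² / 0.10², which rounds up to 102 per arm.

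The present point does not depend on this.

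**Step 4: illustration for debridement (assumed rates).** Suppose the irrigant has no effect, but unequal debridement alone makes the arms differ by b. With n = 100 per arm, p₁ the control rate, p₂ = p₁ − b and p̄ their mean:

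- SE₀ = √(2p̄(1−p̄)/n); SE₁ = √([p₁(1−p₁) + p₂(1−p₂)]/n)
- rejection probability = Φ((b − 1.96·SE₀)/SE₁) + Φ((−b − 1.96·SE₀)/SE₁)

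For p₁ = 12.5% and b = 2 points, p̄ = 0.115, SE₀ = 0.0451 and SE₁ = 0.0451. The terms are Φ(−1.52) + Φ(−2.40) = 0.065 + 0.008 = 0.073.

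| Assumed control SSI | b = 0 | b = 2 points | b = 3 points | b = 5 points |
|---|---|---|---|---|
| 12.5% | 5% | 7.3% | 10.4% | 21.7% |
| 20% | 5% | 6.5% | 8.5% | 15.3% |
| 30% | 5% | 6.1% | 7.6% | 12.4% |

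Neither b nor the control rates come from the documents.

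**Step 5: illustration for grading (assumed mix and risks).** I read the repeated grade II in I.1 and VII.7.d as II and III. Assume grades I/II/III make up 30/40/30% of patients, with infection risks of 5/12/25%. In one arm only, a fraction m of type II is recorded as type III:

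- risk in recorded type III = (0.30·0.25 + m·0.40·0.12)/(0.30 + m·0.40)
- m = 0: 25%; m = 0.1: 0.0798/0.34 = 23.5%; m = 0.2: 0.0846/0.38 = 22.3%
- overall risk in that arm = 0.30·0.05 + 0.40·0.12 + 0.30·0.25 = 13.8%, whatever m is

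Misgrading changes the grade-specific risks and leaves the arm's overall rate alone, which confirms the table in step 2.

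**The case against.** Several objections carry weight.

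- **Randomisation still protects baseline balance.** A reader might infer that the irrigant comparison is confounded. The documents do not support that: nothing shows that surgeons would debride differently by arm, and VII.2.c–d require standard debridement and management in both. This safeguard is weak without criteria, but it exists. The accurate term is a risk of performance bias.
- **Intraoperative grading is an inference.** A reader might take II.3 to mean that the surgeon grades severity in theatre with the arm known. It says only that fixation depends on severity and contamination. What the text shows is that the time, assessor and system of grading are unspecified.
- **The severity analysis treats grade as the exposure.** VII.7.d asks how grade affects deep infection. No grade-by-irrigant interaction is stated and the covariates are not listed, so it goes too far to say that every grade-based result is biased.
- **Delaying the envelope until debridement is finished would clash with VII.2.b.** That section assigns the solution for debridements as well as irrigations at the open fracture. The documents do not separate a debridement stage without irrigant from a later irrigation stage.
- **Repeat debridements are unblinded under any timing**, because one solution is used throughout. The number of debridements therefore stays open to influence.

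These points narrow the concern and constrain the fix. They do not remove it: the arm can be known before the first debridement, and the stated difficulty of blinding participants and research personnel does not explain why it has to be.

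**Conclusion.** The point holds as an avoidable risk at the index operation. As written, the plan lets the surgeon know the arm before the initial debridement and leaves open whether grade is recorded before or after allocation. The first can bias the irrigant comparison. The second can cause differential misclassification in the VII.7.d analysis and the I.1 subcohorts, but cannot change the unadjusted primary test.

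The size and direction of any bias cannot be derived from the documents. On the assumed rates, a 2-point shift inflates the false-positive rate modestly (6.1–7.3%), while a 5-point shift inflates it substantially (12.4–21.7%). A reader might infer that the trial is invalid or that bias has been shown, and neither follows. This is an inexpensive design improvement that leaves part of the exposure in place.

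**What to change.** Amend VII.2.a so that:

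1. consent and eligibility are confirmed before theatre;
2. the severity grade is recorded before the envelope is opened, with the assessor and classification system named;
3. the next numbered envelope is opened in the operating room immediately before the first use of study irrigant. The wording should not prescribe the operative sequence.

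Reconcile this wording with VII.2.b, which ties the assigned solution to debridements as well as irrigations. State in VII.7.d and I.1 that the pre-allocation grade is the one analysed.

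**Cost.** Protocol wording and a later point of envelope opening. The existing envelopes serve, and no patients, staff or procedures are added. Both solutions must be at hand at the first operation.

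**Limits.** Any debridement after the first use of irrigant, and all repeat debridements, still take place with the arm known. The pre-allocation grade may also differ from one assigned later in the operation.

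### The 6-month fracture-healing score has no rule for amputation or unplanned re-operation, so the comparison between arms can be diluted

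*Combined protocol and SAP*

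**What the plan says.** Fracture healing at 6 months is the first secondary objective in section I.2. Section VII.3.b gives the scale: "Tibia radiographs will be collected at each visit per SOC to assess fracture healing as 0-not healed; 1-partially healed; or 2-completely healed". Section VII.7.b gives the time point and test: "Fracture healing at 6 months post-op – compared between groups using a rank sum test".

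Four other places bear on the point.

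- Section VII.2.a is the only place that describes further surgery: "They will return to the operating room for as many operative debridements as necessary until the definitive fixation surgery is performed". It stops at definitive fixation. Nothing covers a later operation for infection or nonunion, and amputation is not mentioned.
- Section VII.4 deals with incomplete follow-up: "Subjects will be removed if they do not return to their follow-up visits or do not complete the study specific tasks". No analysis population, missing-data method or worst-rank rule is given.
- Section VII.3.c says "Deep infection rate as well as wound healing will be assessed", but does not connect infection to the healing score.
- Section V admits any adult with an "Open tibia fracture" who meets the other criteria, with no limit on severity.

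**The concern.** A radiographic grade exists only if there is a tibia to film, and it records the state of the bone on that day, not how it got there. A subject whose limb is amputated before 6 months has no value and falls out of the rank sum test. A subject whose fixation failed and who was re-operated to obtain union can be graded 2, the same as one who healed after the index fixation.

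Neither is ordinary missing or noisy data. Both events can follow deep infection, the outcome the trial hopes to change. If Irrisept works, saline should have more of them, so poor results would be removed or graded at the top more often in the worse arm.

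Section VII.1.a adds that "There is no blinding to the randomization", and no blinded reading of films is described. A scoring rule settled after the data are in would be chosen by people who know the allocation.

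**Working it through.** **Plan's own figure.** There is none for healing. The sample size in section VI ("We plan to enroll 230 participants (n=230 subjects) (100 subjects per group, 30 screen fails) for a 2-year study") rests on 90-day SSI, and this point does not depend on it. It supplies only the 100 per arm used in the simulations.

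**Assumed inputs.** The documents give no failure, amputation, re-operation or healing rates. Let f be the proportion of an arm with a failure, a the share of failures amputated before 6 months, and r the share re-operated and united by 6 months. The remaining failures are graded 0 or 1 in the ratio 70:30. U is the 0/1/2 distribution among everyone else.

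**Formulas.**
- As written: grade 0 = (1−f)U0 + 0.7f(1−a−r); grade 1 = (1−f)U1 + 0.3f(1−a−r); grade 2 = (1−f)U2 + fr; each divided by 1−fa because amputees drop out.
- Both events scored 0: add f(a+r) to grade 0, take fr out of grade 2, and do not divide.
- Effect = P(Irrisept grade > saline grade) + 0.5 P(tie). A value of 0.5 means no difference; above 0.5 favours Irrisept.

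**Step 1: bounding cases.** f = 15% saline and 5% Irrisept; U = 20/30/50%.
- Every failure dropped (a = 1): completely healed is 50% in both arms; rank-sum rejection rate about 5%, so no signal.
- Every failure graded 2 (r = 1): 0.50×0.85 + 0.15 = 57.5% saline and 0.50×0.95 + 0.05 = 52.5% Irrisept. The direction is wrong; rejection rate about 10%.
- Every failure scored 0: 0.50×0.85 = 42.5% and 0.50×0.95 = 47.5%; rejection rate about 18%.

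**Step 2: a mixed case.** Same f and U, with a = 10% and r = 20%.
- Saline as written: (0.2435, 0.2865, 0.4550)/0.985 = 24.7/29.1/46.2%.
- Irrisept as written: (0.2145, 0.2955, 0.4850)/0.995 = 21.6/29.7/48.7%.
- Effect as written: 0.518.
- Amputation alone scored 0: saline 25.85/28.65/45.50%, Irrisept 21.95/29.55/48.50%; effect 0.522.
- Both events scored 0: saline 28.85/28.65/42.50%, Irrisept 22.95/29.55/47.50%; effect 0.535.

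The direction is right throughout. Rejection is about 8% as written and about 15% with both events scored 0.

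**Step 3: higher failure rates.** f = 25% and 15%; U = 10/30/60%.

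| a, r | Effect as written | Both scored 0 | Rejection, as written / both 0 |
|---|---|---|---|
| 10%, 20% | 0.524 | 0.541 | 10% / 20% |
| 30%, 50% | 0.498 | 0.544 | 4% / 22% |
| 30%, 70% | 0.484 | 0.545 | 7% / 22% |

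**Step 4: where the difference vanishes.** With the Step 3 inputs, the effect as written falls to 0.5 once r reaches 66.5% (a = 0), 59.5% (a = 10%) or 46.5% (a = 30%). If only 30% of the other patients are completely healed, the thresholds are 41.5%, 37.5% and 29%; if 80% are, they are 82%, 73.5% and 57.5%. Dropping amputees alone, at 10–30% of failures and r = 0, gives 0.537–0.531 in the 60% case: smaller, but neither gone nor reversed.

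**Step 5: low failure rates.** With f = 5% and 2% and failures scored 0, completely healed is 0.50×0.95 = 47.5% and 0.50×0.98 = 49%. Rejection is only about 6–7%, and about 5% if failures are graded 2.

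**The case against.** A reader might infer that the plan credits re-operated tibiae as healed and that the healing comparison is therefore biased to null or reversed. The documents do not support that. They are silent on both events; the treatment described here is what a film-only score yields when no rule is added, and an assessor could choose to enter 0 for an amputated limb. Reversal appears only under extreme assumptions. The bounding cases make every failure an amputation or a successful re-operation and leave out failures still ununited at 6 months, which the scale already grades low.

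It can also be said that whether the fracture is healed at 6 months, by whatever treatment, is a legitimate question, and that a united tibia is truthfully graded 2. Forcing such a tibia to 0 in the main test would let a discretionary decision by an unblinded team determine the score. That stands, and it is why re-operation belongs in a supporting analysis.

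Two more points stand in part. An excess of infection would be visible in the primary comparison (VII.7.a), though that does not show how many healing scores it affected. Power for healing is low under any rule, so the gain is chiefly an interpretable direction and visible failure counts.

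The amputation gap survives all of this: no film-based grade exists for that subject, and no section supplies one.

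**Conclusion.** The concern holds as an unspecified rule with a foreseeable, infection-related direction. The likely consequence is dilution: 0.518 against 0.535 in the mixed case at 15% and 5% failures, and roughly halved rejection rates there (8% against 15%) and in the milder case at 25% and 15% (10% against 20%). Masking or reversal requires many failures to be both re-operated and united by 6 months, with thresholds from 29% to 82% of failures across the assumptions tried. At failure rates near 5% and 2% the matter is negligible.

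Every event and healing rate is an assumption. The 5%, 18% and 10% rejection rates bound the problem and do not predict it. The 90-day SSI primary endpoint is unaffected. The point is worth acting on because the remedy is nearly free and is credible only if fixed before the data are examined.

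**What to change.** Add to sections VII.3.b and VII.7.b: *Amputation of the study limb before the 6-month visit is scored 0 (not healed), and the subject stays in the rank sum test despite VII.4.*

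Record any unplanned re-operation at the study tibia, whether for infection or to promote union, and report counts of amputation and of re-operation by arm.

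Pre-specify a supporting rank sum analysis that also scores subjects with such a re-operation as 0, and present it beside the radiographic grade. The amputation rule alone recovers only part of the dilution (0.518 to 0.522 in the mixed case), so the supporting analysis is needed to show the rest.

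The cost is one form field and one extra analysis, and the main score is no longer purely radiographic for amputees. Only scoring and reporting change; clinical care does not.
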